Visit Number	UP b	1	2	3	4	5	6	7	8	9	10	11 c	12 c	13 c	14 c	15	801 d	802 d	UV	ED	ED only if participant has completed V1 and received IP in Part B.
Weeks Relative to Baseline (V1)		0	4	8	12	16	20	24	28	32	36	40	44	48	60	72	84	96	997		Procedures for some visits may take more than 1 day.
Visit Interval Tolerance (days)		—	-7 to +10	±7	±7	±7	±7	±7	±7	±7	±7	±7	±7	±7	±7	±7	±7	±7			
12-lead ECG (central or local)		X			X			X			X			X	X				X		Perform prior to administration of IP, when appropriate. ECG at V14 not required for participants who completed dosing at V10.

		Part B: Open-Label															Part B: Follow-Up, UV, ED				Comments		
		Visit Number	UP b	1	2	3	4	5	6	7	8	9	10	11 c	12 c	13 c	14 c	15	801 d	802 d	UV	ED	
Weeks Relative to Baseline (V1)		0		4	8	12	16	20	24	28	32	36	40	44	48	60	72	84	96	997			Procedures for some visits may take more than 1 day.
Visit Interval Tolerance (days)		—		-7 to +10	±7	±7	±7	±7	±7	±7	±7	±7	±7	±7	±7	±7	±7	±7	±7	±7			
PET Scans and MRI																							Perform prior to V1 at UP if last recorded MRI from originating study occurred >12 months before V1.
MRI			X		X		X					X					X				X		MRI at V2 is to be performed and reviewed prior to V2 infusion and may occur no sooner than 21 days after the first infusion. If infusions are suspended after the first, second, or third dose, an MRI is to be performed and reviewed prior to the fourth infusion.  MRI at V4 is to be performed and reviewed prior to V4 infusion.  MRI at V4 may occur 14 days before the scheduled visit date without protocol deviation.

		Part B: Open-Label															Part B: Follow-Up, UV, ED				Comments			
		Visit Number	UP b	1	2	3	4	5	6	7	8	9	10	11 c	12 c	13 c	14 c	15	801 d	802 d	UV	ED		
Weeks Relative to Baseline (V1)		0		4	8	12	16	20	24	28	32	36	40	44	48	60	72	84	96	997			Procedures for some visits may take more than 1 day.	
Visit Interval Tolerance (days)		-		-7 to +10	±7	±7	±7	±7	±7	±7	±7	±7	±7	±7	±7	±7	±7	±7	±7	±7				
Florbetapir F 18 PET scan													X									X e	Florbetapir F 18 PET scan may occur ±14 days from scheduled visit date without protocol deviation.	
Clinician-Administered Assessments (Electronic)																								

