### 3. Objectives and Endpoints

Objectives	Endpoints
Primary	
Part A To evaluate the reliability of VTC compared with on-site administered cognitive and functional measures	The intraclass correlation between VTC and on-site assessment for PAIR 1 for 
 
• ADAS-Cog13
 
• ADCS-ADL
 
• MMSE
 
• CDR-SB
 

Part B To evaluate safety and tolerability of donanemab	Standard safety assessments in Part B: 
 
• Spontaneously reported AEs
 
• Clinical laboratory tests
 
• Vital sign and body weight measurements
 
• 12-lead ECGs
 
• Physical and neurological examinations
 
 MRI (ARIA and emergent radiological findings) Infusion-related reactions C-SSRS
Secondary	
To assess the effect of donanemab on clinical progression in participants with symptomatic AD	Change from baseline up to Week 72 as measured in Part B by: 
 
• MMSE score
 
• ADAS-Cog13 score
 
• iADRS score
 
• ADCS-iADL score
 
• CDR-SB
 

To assess the effect of donanemab on brain amyloid deposition	Change in brain amyloid plaque deposition from baseline at Week 36 of Part B as measured by florbetapir F 18 PET scan
To assess the effect of donanemab on brain region volumes	Change in volumetric MRI measures from baseline to Week 72 in Part B
To assess peripheral PK and presence of anti-donanemab antibodies	PK of donanemab in Part B. ADAs against donanemab in Part B including 
 
• treatment-emergent ADAs
 
• neutralizing antibodies
 

Tertiary/Exploratory	

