### 8.2.5. Magnetic Resonance Imaging

MRI of the brain will be performed according to the SoA (Section 1.3) and as clinically indicated. Unscheduled MRIs may be performed at the discretion of investigator.

This technology will be used to check for evidence of ARIA-H or ARIA-E and safety findings (volumetric MRI will also be used to calculate brain volumes, as noted in Section 8.8).

The MRI scans will be reviewed by the investigator or qualified designee for immediate participant management. Any clinically significant findings noted that result in a new or updated diagnosis should be recorded as an AE. After the MRI scan is read locally, the MRI scans will be sent for analysis to a centralized MRI vendor designated by Lilly. The centralized MRI vendor's interpretation of the participant's final MRI from the originating study or unscheduled MRI performed in Study AACH prior to Part B will determine final MRI eligibility for Part B.

Specific analyses of the scans, including assessments of ARIA-H and ARIA-E and calculations of brain volumes, will be interpreted by the centralized MRI vendor for data analysis and report writing purposes.

Results of centrally read MRIs regarding participant care/safety will be reported back to sites.

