### **Volumetric MRI**

Effects on regional brain volumes, as assessed by volumetric MRI, will be performed according to the SoA (Section 1.3). Donanemab effects on volumetric MRI will be assessed to evaluate the loss of brain volume that occurs in AD patients.

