### 9.2. Sample Size Determination

Approximately 200 participants will be enrolled and randomized in a 1:1 ratio to the 2 groups (Group 1: Cognitive/functional scale assessment on-site, followed by VTC assessment; or Group 2: Cognitive/functional scale assessment by VTC, followed by assessment on-site). It is expected that approximately 180 participants will complete Pair 1 of Part A. Approximately 150 participants are expected to complete the study.

A correlation coefficient of 0.80 between on-site and VTC assessment is assumed.

Furthermore, it is assumed that the 2 modalities will yield similar means but different standard deviations. A mean ADAS-Cog13 total score of 27.2 and a SD of 8 and 9 were used for the power calculation. These estimates were derived from Studies I8D-MC-AZES, I8D-MC-AZET, and H8A-MC-LZAX, all reflecting an early or mild AD population.

This sample size will provide approximately 81% power to demonstrate 'acceptable' reliability, defined as the lower limit of the 95% confidence interval for ICC above 0.70.

This power calculation is based on the ADAS-Cog13, as this is the scale anticipated to have most scale adaptations and most variability from on-site to VTC assessment. Other scales should therefore demonstrate equal or greater power for these comparisons.

Simulations (carried out in R) with 1000 iterations, utilizing above described assumption, yields an average ICC of 0.793 and average 95% confidence interval of 0.732 to 0.841.

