### 9.4.3. Secondary Endpoint(s)

To assess the effect of donanemab on clinical progression in participants with symptomatic AD, MMRMs will be fit to the Part B data up to Week 72 for ADAS-Cog13, ADCS-ADL, iADRS, MMSE, and CDR-SB. The models will include terms for visit, age, years of education, and presence/absence of anti-dementia drugs. Visit will be considered a categorical variable.

Observed case analyses will also be conducted for each scale. Additionally, if participant numbers are adequate, AD progression from these models can be compared to anticipated progression had the patient remained untreated. Details of such a comparison are contained in the SAP.

Change from baseline in brain amyloid deposition at Week 36 and Week 72 of Part B will be assessed using an MMRM. The model will include terms for visit, age, years of education, and presence/absence of anti-dementia drugs. Visit will be considered a categorical variable. An observed case analysis will also be conducted.

Change from baseline in brain region volumes at Week 72 for Part B will be assessed using an ANCOVA model. The model will include terms for age, years of education, and presence/absence of anti-dementia drugs. An observed case analysis will also be conducted. The brain regions of interest will be defined in the SAP.

PK analyses will be defined by the PK scientist and will be specified in the PK analysis plan.

Categorical displays of ADAs against donanemab and neutralizing antibodies will be presented.

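### The Week 72 brain-volume analysis is a single-visit ANCOVA with no rule for a missing Week 72 volume, although earlier MRIs are scheduled and the clinical scales get a repeated-measures model

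*Protocol*

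**What the plan says.** The endpoint in Protocol section 3 is "Change in volumetric MRI measures from baseline to Week 72 in Part B". Protocol 9.4.3 gives the analysis: "Change from baseline in brain region volumes at Week 72 for Part B will be assessed using an ANCOVA model". It continues: "The model will include terms for age, years of education, and presence/absence of anti-dementia drugs. An observed case analysis will also be conducted". There is no visit term, no earlier volume in the model and no rule for a missing Week 72 value.

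In the same section the clinical scales are analysed to Week 72 by MMRM with visit as a categorical term. For amyloid, "Change from baseline in brain amyloid deposition at Week 36 and Week 72 of Part B will be assessed using an MMRM". No reason is given for treating volume differently.

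On timing, Protocol 8.8 (Volumetric MRI) says: "Effects on regional brain volumes, as assessed by volumetric MRI, will be performed according to the SoA". The Part B schedule has a single MRI row and does not separate safety scans from volumetric ones. Visits 2 and 4 are explicit; for example, "MRI at V2 is to be performed and reviewed prior to V2 infusion". The row also appears to carry marks at about Week 36 and at early discontinuation. Protocol 7.1 supports the latter, since it waives the MRI among end-of-study procedures for participants with an MRI-incompatible device.

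Protocol 9.4.3 leaves the choice of brain regions to the SAP. The SAP lists the endpoint in its objectives table, but its Part B section has no volumetric analysis and names no regions. SAP 5.1 sets a general rule for change from baseline: a baseline and at least one later value.

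**The concern.** A one-visit ANCOVA on age, education and anti-dementia drug use cannot adjust for how a participant's volume was changing before the participant left. The Week 72 volume is missing for those who withdraw, die, miss the scan or receive an MRI-incompatible device. The text allows two ways of handling them:

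- **Observed Week 72 scans only.** The estimate describes those who stayed. It is biased if leaving is related to volume change.
- **Last scan carried forward.** Everyone with a later scan is scored, but an early scan stands in for Week 72. Where volume loss accumulates, this understates it.

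Part B has one arm, so no control group shares the bias and cancels it; the error goes straight into the reported mean. The choice between the two is also left open in an open-label study whose data the sponsor can see continually (Protocol 9.5, SAP 5.3).

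**Working it through.** **No planned figure to reproduce.** The documents give no sample size, SD, expected change or dropout rate for this endpoint. The only power statement concerns Part A.

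**Attrition.** Protocol 9.2 expects 200 randomized and about 180 completing Pair 1, and states: "Approximately 150 participants are expected to complete the study". So 1 − 150/200 = 25%, and 1 − 150/180 = 16.7%. Neither is a Part B Week 72 rate:
- both pool Parts A, B and C;
- the 25% includes the 20 not expected to finish Pair 1, most of whom would never be dosed;
- completing the study means reaching the last required visit (Protocol 4.4), which in Part B can be Week 96.

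Participants who only stop study drug remain in the study (Protocol 7.1), so they can still have a Week 72 scan. A 10% rate is therefore shown as well.

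**Assumed inputs** (none from the documents): 80 participants; individual slopes with mean −1 and SD 0.5 per 36 weeks, so a true Week 72 change of −2.0; measurement SD 0.3; one earlier volume at Week 36; log-odds of leaving that change by 0.5 to 1.0 per SD of the Week 36 change. These imply:
- SD of the Week 72 change = √((2 × 0.5)² + 0.3²) = 1.04;
- correlation of the Week 36 and Week 72 changes = (2 × 0.5²) / (√(0.5² + 0.3²) × 1.04) = 0.50 / (0.58 × 1.04), about 0.82.

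**Formulas.** With a fraction p leaving:
- observed-only bias = p × (mean of stayers − mean of leavers), evaluated by simulation;
- carry-forward bias under random dropout = p × (2.0 − 1.0)/2.0 = p/2 of the change;
- the MMRM-type estimate shifts the stayers' Week 72 mean by the regression of Week 72 on Week 36, evaluated at the full-sample Week 36 mean.

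| Dropout | Observed Week 72 only, leaving related to volume | Same, in standard errors | Carry-forward, random dropout | MMRM-type, missing at random |
|---|---|---|---|---|
| 10% | 2–4% | 0.3–0.65 | 5% | about 0 |
| 17% | 3.5–6.3% | 0.5–1.0 | 8.3% | about 0 |
| 25% | 5–9% | 0.8–1.4 | 12.5% | about 0 |

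The observed-only column understates loss if faster losers leave, and overstates it by the same amount if slower losers leave. It is zero if leaving is unrelated to volume. When faster losers leave, the nominal 95% interval from observed scans covers 91–82% of the time at 17% dropout and 87–70% at 25%.

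**Not-at-random dropout.** If leaving depends on the unseen Week 72 value, the MMRM-type estimate is off by about 1–4% across these dropout rates, against 3–11% for observed scans only.

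**Sensitivity to the inputs.** The percentages depend on the ratio of SD to mean change, here 1.04/2.0. With a true change of only 1 SD, a correlation of 0.5 or 0.8 and a log-odds slope of 0.7, at 17% or 25% dropout:
- observed-only bias is 0.05–0.13 SD (5–13% of the change) under missing at random and 0.11–0.16 SD under not-at-random dropout, in either direction;
- the MMRM-type estimate is again about 0 under missing at random and 0.04–0.12 SD under not-at-random dropout;
- carry-forward understates loss by 0.04–0.19 SD in every setting.

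**The case against.** A reader might infer that early leavers cannot be scored and that the ANCOVA is a completers analysis. The documents do not establish this. Protocol 9.4.3 lists an observed-case analysis in addition to the ANCOVA, which suggests the ANCOVA may be something else. The SAP 5.1 inclusion rule does not require a Week 72 value. What the text shows is a missing rule. That part of the objection stands, but neither candidate rule is satisfactory.

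A reader might also infer that volume loss will be understated. That needs faster losers to leave more often, and nothing in the documents links dropout to atrophy. With the opposite pattern the sign reverses. Only carry-forward understates loss without any such link.

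Four further points stand as limits:
- The MMRM's near-zero bias comes from generating dropout from the observed Week 36 value. It does not carry over to not-at-random dropout. The model also implies Week 72 volumes for participants who died.
- The Visit 2 and Visit 4 scans have a safety purpose (ARIA), and the documents do not say that they yield volumes. The gain may rest mainly on the scan at about Week 36.
- The Week 36 and early-discontinuation marks should be confirmed against the formatted schedule, because the columns of the text we worked from are misaligned.
- Part B has no statistical hypotheses and its primary objective is safety, so the stakes are limited.

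**Conclusion.** The point holds as a weak choice of model together with an unstated missing-data rule. Participants are scanned before Week 72, and the plan uses none of those volumes for a secondary endpoint, while its clinical scales get a model that would.

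The size cannot be fixed from the documents. On the main assumed inputs, observed-only bias is about 2–9% of the change for dropout of 10–25%, up to 1.4 standard errors with 80 participants, in either direction. With a smaller change relative to its SD, the percentages are larger. Under those main inputs an MMRM does no worse in any setting examined: about 0% under missing at random, about 1–4% under not-at-random dropout, and slightly more precise when dropout is harmless.

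Severity is minor to moderate. The endpoint is an uncontrolled secondary biomarker, no test depends on it, and participants who only stop study drug are still followed.

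**What to change.** In Protocol 9.4.3 and the SAP:

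1. Replace the Week 72 ANCOVA with an MMRM on change in regional volume over the scheduled post-baseline MRIs that yield volumes. Keep the same covariates, add categorical visit, and use the Week 72 least-squares mean as the estimate. State which visits supply volumes.
2. Assign early-discontinuation scans to a scheduled MRI visit by actual date within prespecified windows, with no carry-forward. A bare nearest-visit rule is not enough: with MRI visits at Weeks 36 and 72, every scan after Week (36 + 72)/2 = 54 would count as Week 72. State the width of the Week 72 window and what happens to a scan outside every window.
3. Keep the Week 72 observed-case ANCOVA as a sensitivity analysis, and add one that allows not-at-random dropout.
4. Put the volumetric analysis and the brain regions into the SAP, which has neither, and report how many Part B participants have no Week 72 volume and why.

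The cost is wording and extra volume processing of scans the schedule already requires; no visits or scans are added. The main estimate would then rely on missing at random, which item 3 is there to probe.

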### 9.4.4. Tertiary/Exploratory Endpoint(s)

As a sensitivity analysis for the primary endpoint of Part A, to assess whether the VTC clinical assessment includes any bias relative to the on-site clinical assessment, an ICC looking at the consistency of the 2 measures will be calculated – ICC(C,1) per McGraw and Wong (1996). By definition, the consistency ICC will be equal to or larger than the ICC for absolute agreement. Large differences between the absolute agreement and consistency ICCs suggest a shift (upward or downward) in the VTC relative to the on-site assessment.

Using the same ANOVA model specified in Section 9.4.2, the ICCs and 95% confidence intervals for the second pair and third pair of on-site and remote clinical assessments will be estimated. Comparisons between the ICCs from the first pair of assessments and the second and third pairs of assessments will be made to measure consistency across measures. If fewer than 50 pairs of clinical assessments are collected for Pairs 2 or 3, only descriptive statistics will be reported. See the SAP for further details.

To compare disease progression as measured by VTC versus on-site, an MMRM will be fit to the clinical assessment measures. Observations will be grouped by test modality (VTC and on-site).

The MMRM will include terms for modality, visit, visit-by-modality interaction, age, years of education, and presence/absence of anti-dementia drugs. Visit will be considered a categorical variable. The null hypothesis is that the contrast between the VTC modality versus the on-site modality at each visit equals 0. An unstructured covariance matrix will be used to model the within-subject variance-covariance errors. If the unstructured covariance structure matrix results in a lack of convergence, the following tests will be used in sequence:

- heterogeneous Toeplitz covariance structure
- heterogeneous autoregressive covariance structure
- heterogeneous compound symmetry covariance structure
- compound symmetry covariance structure

The Kenward-Roger approximation will be used to estimate the denominator degrees of freedom.

Changes in the blood-based biomarkers of NfL, P-tau, and A $\beta$  during Part B will be summarized with observed case analyses.

For participants in Part C of the study, the interest is whether the changes in brain amyloid deposition, brain tau deposition, and clinical progression of AD for participants who received donanemab in the originating study are maintained after donanemab treatment is removed. For each of these endpoints, change from the last observation of the originating study will be fit using an ANCOVA model including terms for age, years of education, and presence/absence of anti-dementia drugs. Observed case analyses will also be presented.

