### 9.4. Statistical Analyses

#### 9.4.1. General Considerations

Statistical analysis of this study will be the responsibility of the sponsor or its designee.

Unless otherwise noted, statistical tests will be conducted at a 2-sided alpha level of 0.05 and 95% confidence intervals will be displayed as 2-sided.

No adjustments for multiple comparisons are planned.

All analyses involving calculation of ICCs will be limited to the Efficacy Evaluable population, requiring participants to contribute complete pairs of on-site and remote clinical assessments to be included. The ICC will be calculated as 2-way mixed-effect model looking for absolute agreement across multiple raters, with raters defined as on-site assessment and VTC assessment. See Section 9.4.2 below and the SAP for further specification of the analysis.

If either ADAS-Cog13 or ADCS-iADL is missing, iADRS score will be considered missing.

Baseline definitions are dependent on the quantity being assessed. For TE safety analyses, only participants who have both a baseline observation and a postbaseline observation will be included in the analysis for each analyte or parameter, respectively. The SAP will define baselines where needed.

A database lock is expected to occur after all randomized participants have completed participation in Part A of the study. Analyses related to the validation of remote assessments compared to on-site assessments will be conducted. As no IP is administered during Part A, safety analyses will be limited.

Any change to the data analysis methods described in the protocol will require an amendment only if it changes a principle feature of the protocol. Any other change made to the data analysis methods described in the protocol, and the justification for making the change, will be described

in the SAP and the clinical study report. Additional exploratory analyses of the data will be conducted as deemed appropriate.

The SAP will be finalized prior to first participant visit and will include a more technical and detailed description of the statistical analyses described in these sections.

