6.5. Primary Objective

The primary objective of Part A of this study is to evaluate the reliability of VTC compared with on-site administered cognitive and functional measures. This will be assessed by estimating the intra-class correlation (ICC) and the associated 95% confidence interval for the first pair of

observations from participants and comparing the lower bound of the confidence interval to 0.70, the ICC cut-off for acceptable reliability.

Using the guidelines and notation for defining ICCs published by McGraw and Wong (1996), the ICC of primary interest for this study is a 2-way mixed model, interaction absent, with single measurements from each modality on participants, looking at absolute agreement – ICC(A,1). In the present study, the ‘raters’ are the two modalities by which the clinical scales are assessed, on-site and VTC. As we are interested in comparing these specific modalities, modality is considered a fixed effect.

For ADAS-Cog₁₃ total score, ADCS-ADL total score, iADRS total score, CDR Sum of Boxes, and MMSE total score, individual mixed models will be fit to the data with fixed effects of modality, time effect, age, years of education, and presence/absence of anti-dementia drugs and a random effect for subject. ICCs will be estimated using the mean squares from these models and defined as:

Absolute Agreement: $ICC (A,1) = (MS_{subj} - MS_{error}) / (MS_{subj} + MS_{error} + 1/n(MS_{modality} - MS_{error}))$

Consistency: $ICC (C,1) = (MS_{subj} - MS_{error}) / (MS_{subj} + MS_{error})$

95% Confidence intervals for these quantities will be constructed as specified in Table 7 of McGraw and Wong (1996).

Similar analyses will also be conducted for pairs 2 and 3 of each of the clinical outcomes specified above. As the number of subjects contributing additional pairs may be limited, no specific hypothesis/test is specified.

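### The planned ICC-gap check for VTC bias gives no direction and has no yardstick; report the Pair 1 VTC minus on-site difference with its 95% CI

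*Protocol*

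**What the plan says.** Protocol 9.4.4 plans the consistency ICC, ICC(C,1), as a sensitivity analysis for the Part A primary endpoint. Its declared aim is to find out whether VTC assessment carries any bias relative to on-site assessment. It is to be read against the primary absolute-agreement ICC, ICC(A,1): "Large differences between the absolute agreement and consistency ICCs suggest a shift (upward or downward) in the VTC relative to the on-site assessment". The sentence before that says: "By definition, the consistency ICC will be equal to or larger than the ICC for absolute agreement". No value for large is given, and no interval or test for the difference between the two ICCs.

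SAP 6.5 prints both ICC formulas but no rule for reading the gap. It does specify the Pair 1 model: "individual mixed models will be fit to the data with fixed effects of modality, time effect, age, years of education", with anti-dementia drug use as a further fixed effect and subject as a random effect. Protocol 9.4.2 lists the same fixed effects. Neither document commits to reporting the estimated modality effect from that model with a confidence interval.

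Two other planned analyses touch modality. Protocol 9.4.4 and SAP 6.6 fit an MMRM with modality, visit and their interaction, and test the VTC versus on-site contrast at each visit against zero. The primary criterion (Protocol 9.4.2, SAP 6.5) requires the lower 95% limit of ICC(A,1) to exceed 0.70.

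**The concern.** Part A is meant to show whether VTC and on-site scores can stand in for each other. A later trial that mixes modalities needs the size and sign of any systematic offset. The statistic named for that job is unsigned, is expressed in ICC units rather than scale points, and is judged by an undefined word. Two analysts could look at the same gap of 0.02 and reach opposite conclusions, and neither could say whether VTC scores run high or low. The quantity that answers the question is already a term in the fitted model.

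**Working it through.** **Inputs, from Protocol 9.2 and 9.4.1**

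- Pairs: "It is expected that approximately 180 participants will complete Pair 1 of Part A".
- Allocation: "Approximately 200 participants will be enrolled and randomized in a 1:1 ratio to the 2 groups", so about 90 per order group among 180 completers.
- Correlation: "A correlation coefficient of 0.80 between on-site and VTC assessment is assumed".
- ADAS-Cog13 mean and SDs: "total score of 27.2 and a SD of 8 and 9 were used for the power calculation".
- Level: "statistical tests will be conducted at a 2-sided alpha level of 0.05 and 95% confidence intervals will be displayed as 2-sided".
- Shift: the protocol assumes similar means. Shifts of 1 to 4 points are assumptions made here to show a range.

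**The plan's own figures.** Simulating 20,000 bivariate-normal samples of 180 pairs, without covariates, gives a mean ICC(A,1) of 0.793 and a mean 95% CI of 0.732 to 0.841, as stated in Protocol 9.2. Power is 82.4% to 82.8% over two runs, against the stated 81%. With 150 pairs power is 75% and with 200 it is 86%, so the stated figures belong to 180 pairs.

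**Size of the gap.** The covariance is 0.80 × 8 × 9 = 57.6 and the average variance is (64 + 81)/2 = 72.5. For a shift d:

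- ICC(C,1) = 57.6/72.5 = 0.794, whatever d is.
- ICC(A,1) = 57.6/(72.5 + d²/2).
- At d = 2 the gap is 57.6/72.5 − 57.6/74.5 = 0.794 − 0.773 = 0.021.

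Only d² appears, so +2 and −2 give the same gap. These figures use a multiplier of 2/n on the modality term. With the 1/n multiplier printed in SAP 6.5, the 2-point gap falls to about 0.011.

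| Shift (points) | Gap | 95% range of gap, n = 180 | Samples with negative gap | Primary criterion met | Power, paired difference | Power, MMRM contrast at one visit |
|---|---|---|---|---|---|---|
| 0 | 0 | −0.001 to 0.004 | 68% | 82% | 5% (the test level) | – |
| 1 | 0.005 | −0.001 to 0.017 | 7% | 73% | 68% | 12% |
| 2 | 0.021 | 0.007 to 0.041 | none | 26% | 99.8% | 35% |
| 3 | 0.046 | 0.025 to 0.073 | none | 0.6% | about 100% | 66% |
| 4 | 0.079 | 0.051 to 0.111 | none | about 0% | about 100% | 88% |

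**How 0.021 would look in a report.** The protocol's expected CI is 0.841 − 0.732 = 0.109 wide. Two ICCs that differ by 0.021 would appear with almost wholly overlapping intervals. That overlap is the wrong yardstick, because both ICCs come from the same data, but the plan supplies no better one. The right one is the no-shift distribution of the gap, whose 95th percentile is 0.0026.

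**Paired difference.** Var(VTC − on-site) = 64 + 81 − 2 × 57.6 = 29.8, so the SD is 5.46 and the SE is 5.46/√180 = 0.41. A 2-point shift is 2/0.407 = 4.9 SE, and the 95% CI is about ±0.80 points (1.96 × 0.407).

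**MMRM contrast at one visit.** Participants alternate modality from their randomized start, so at any visit one order group is on VTC and the other on-site. The contrast is therefore between groups: SE = √(64/90 + 81/90) = 1.27, about three times the paired SE.

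**Ordering of the two ICCs.** In sample estimates ICC(C,1) falls below ICC(A,1) exactly when MS_modality < MS_error. With no shift that has probability P(F(1,179) < 1) = 0.68. The reversal was never larger than about 0.001.

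**The case against.** A reader might infer from 9.4.4 that the ICC gap is the only planned look at VTC bias. It is not. The MMRM in the same section and in SAP 6.6 gives a signed VTC versus on-site contrast, and averaging its contrasts at Visits 602 and 603 would recover the within-person precision of 0.41. The primary ICC(A,1) also falls under a shift: the chance of meeting its criterion drops from 82% to 26% at 2 points.

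A reader might also infer that a real bias would be missed. That does not follow. The sign reversals occur mainly when there is no shift or a small one, and they are negligible in size. At 2 points no simulated gap was negative, and 99.9% exceeded the no-shift 95th percentile. The statistic carries the information; what is missing is a scale to read it on. Nor can one say that the rule would declare a 0.02 gap absent, since no cut-off exists.

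These points stand, but they do not supply the missing estimate. The MMRM is presented as a comparison of disease progression and its stated null is per visit; no averaged contrast is specified. A failed primary criterion cannot separate offset from noise or show direction, and at a 1-point shift the criterion is still met 73% of the time.

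The ordering statement is true of the population ICCs, so the error is one of wording and changes no decision. It is also fair to say that the modality estimate comes out of the fitted model and that SAP 6.1 permits further exploratory analyses. Permission to report it is not a commitment to do so.

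**Conclusion.** The concern holds in a limited form. The named check for VTC bias has no direction and no threshold, and it moves by about 0.005, 0.021 and 0.046 for shifts of 1, 2 and 3 ADAS-Cog13 points, so a gap near 0.02 could be dismissed. The Pair 1 model already contains a signed estimate in scale points with an SE of about 0.41, against 1.27 for a single-visit MMRM contrast, and neither document commits to reporting it with a CI. The claim that the consistency ICC is always at least as large fails in about 68% of no-shift samples, by amounts too small to matter.

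The figures assume bivariate normality, no covariate adjustment, no period effect and equal order groups. The shifts are assumed, and no meaningful ADAS-Cog13 modality shift is given in either document. The primary decision rule is unaffected.

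**What to change.** In SAP 6.5, and in Protocol 9.4.4 at its next amendment:

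- For each scale, name the Pair 1 modality effect (VTC minus on-site) with its 95% CI, from the model in Protocol 9.4.2 and SAP 6.5, as the assessment of bias. Limits of agreement may be added to show the spread of individual differences.
- Keep ICC(C,1) with its CI as supportive, and drop the reading rule based on an undefined large gap.
- Delete the ordering statement, or restrict it to the population ICCs.

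The cost is wording and one extra line per scale in a table. No new data, visits or models are needed.
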